The force value is set by the dental practitioner, based on the same common orthodontic criteria considered in force application in treatment with brackets. Whereas in brackets the force is changed by replacement of, for example, the wires and band attachments, in the Aerodentis system the force is changed by increasing the air pressure within the inflatable element. The value of the applied forces in Aerodentis falls within the optimal force range for conventional orthodontic treatment. In treatment with braces the applied force is usually between 50 to 200 grams and the doctor knows which force to apply according to the specific case. The Aerodentis system is pre-calibrated to apply an average force of 80 grams on all teeth that are in treatment. If needed, the force can be programmed to a lower (50 grams) or higher (100-140 grams) force according to the doctor's decision. For example, in cases of compromised dentition or a particularly sensitive patient, the force can be lowered to 50 grams. In cases of insufficient treatment progress, the doctor can apply a higher force of 120-140 grams, as is often done with conventional treatments. Thus, progressive treatment can be performed without the need to change hardware components or aligner trays.

b. What is the probable length of time required for the entire study (i.e., recruitment through data analysis to study closure)?

24 months

c. What is the total amount of time each participant will be involved?

15 months

d. If different phases are involved, what is the duration of each phase in which the participants will be involved? If no phases are involved, enter "not applicable."

\_\_\_\_\_

e. List the procedures, the length of time each will take, and the frequency of repetition, and indicate whether each is done solely for research or would already be performed for treatment or diagnostic purposes (routine care) for the population. *Insert additional table rows as needed.*

Procedure	Length of Time Required of Participants	Frequency of Repetition	Research (Res) – OR- Routine Care
Screening	10 minutes	once	 Res  Routine
Compliance questionnaire	10 minutes	once	 Res  Routine
Take pictures of teeth for final approval	10 minutes	once	 Res  Routine

Review of photos for establishing pool of participants	24 hours	once	 Res  Routine
Consent	20 minutes	once	 Res  Routine
Fitting of appliance (Aerodentis or Invisalign)	1 hour	once	 Res  Routine
Quality of life questionnaire – Aerodentis	5 minutes	once every 4 weeks	 Res  Routine
Aerodentis device wear	10 hours	daily	 Res  Routine
Clear Correctors wear	24 hours everyday	daily	 Res  Routine

f. Will an interview script or questionnaire be used? Yes No  
**If Yes**, attach a copy.

g. Will participants incur any costs as a result of their participation? Yes No  
**If Yes**, describe the reason for and amount of each foreseeable cost.

Participants will be required to pay \$5000 for Aerodentis, or \$5000 for conventional clear aligners. Participants wearing the Aerodentis device will be ask to pay for treatment to assure compliance use with device. This is the same cost as all other UAB orthodontic patients incur for conventional clear aligner treatment, although, the participants wearing the Aerodentis device will be given compensation because the device is not familiar in the US and as a result the participants have uncertainty regarding its success and efficacy. Participants in the control group will be asked to pay regular price, without compensation, because Invisalign is a familiar treatment in the US and as a result the patient is certain regarding its process and results.

h. Will participants be compensated? Yes No  
**If Yes**, complete i-v:

- i. Type: (e.g., cash, check, gift card, merchandise): Check – Aerodentis group only
- ii. Amount or Value: One check for \$1000, three checks for \$550, one check for \$850
- iii. Method (e.g., mail, at visit): At visit
- iv. Timing of Payments: (e.g., every visit, each month): one check for \$1000 at participant recruitment, three refunds of \$550 each – depending on compliance of a minimum of 10 treatment hours a day, after every two months of treatment, and final refund of \$850 at treatment completion.
- v. Maximum Amount of Payments per Participant: \$3500 - Aerodentis group only

## 17. Describe the potential benefits of the research.

Aerodentis applies pulsating physiological force to move teeth gradually into the desired position and occlusion. It is well established in the literature that pulsating orthodontic force, which mimics the normal, natural physiology of the body, is an effective modality for orthodontic treatment. Subsequent clinical and research data has shown that the application of pulsating force accelerates orthodontic correction, as well as facilitating additional benefits when compared to continuous force. The controlled Individual Force Prescription enables the PIs' to prescribe an accurate force level and pulsating cycle, depending on how orthodontic treatment progresses for each individual. Also with Aerodentis, patients can properly brush and floss and do not have to worry about bothersome food traps, like with wearing braces, which can lead to plaque and tooth decay.

## 18. Risks

- a. List the known risks—physical, psychological, social, economic, and/or legal—that participants may encounter as a result of procedures required in this protocol. Do not list risks resulting from standard-of-care procedures. *Note. Risks included in this protocol document should be included in the written consent document.*

- Gums, cheeks, or lips may be irritated by mouthpiece.
- Failure to wear the appliance for the required treatment time and/or not using the product as directed by your doctor can lengthen the treatment time and affect the ability to achieve the desired results.

b. Estimate the frequency, severity, and reversibility of each risk listed.

Mild, when wearing device. Patient may stop wearing device if risks occur.

c. Is this a therapeutic study or intervention?

Yes No

**If Yes**, complete the following items:

i. Describe the standard of care in the setting where the research will be conducted: The most common standard of care for orthodontic movement of teeth in correcting malocclusion is by providing mechanical forces, involving a system of metal archwires and brackets, typically referred to as orthodontics, and known to many as "braces". The basic system is augmented with elastics, metal bands, headgear, retainers, and other ancillary devices as dictated by the specific treatment. These forces are static in that they are only adjusted at specific visits but then stay constant and do not change between visits.

ii. Describe any other alternative treatments or interventions: Participants may choose not to participate in the Aerodentis clinical trial and continue receiving routine orthodontic treatment at UAB's Department of Orthodontics.

iii. Describe any withholding of, delay in, or washout period for standard of care or alternative treatment that participants may be currently using: N/A

d. Do you foresee that participants might need additional medical or psychological resources as a result of the research procedures/interventions? Yes No

**If Yes**, describe the provisions that have been made to make these resources available.

\_\_\_\_\_

e. Do the benefits or knowledge to be gained outweigh the risks to participants?

Yes No

**If No**, provide justification for performing the research: \_\_\_\_\_

## 19. Precautions/Minimization of Risks

a. Describe precautions that will be taken to avoid risks and the means for monitoring to detect risks.

All aspects of this study will be monitored by the PI, [name] [name], and Co-PIs'. All data will be encrypted and only accessible by the PI. Safety analysis will be performed at every visit, and patients may be ask to stop treatment if adverse events occur.

**If study involves drugs or devices skip Items 19.b. and 19.c., go to Item 20, and complete the Drug or Device Review Sheet, as applicable.**

b. If hazards to an individual participant occur, describe (i) the criteria that will be used to decide whether that participant should be removed from the study; (ii) the procedure for removing such participants when necessary to protect their rights and welfare; and (iii) any special procedures, precautions, or follow-up that will be used to ensure the safety of other currently enrolled participants.

Participants will be removed from the study if any risks are incurred as judged by the PI, [name] [name] or Co-PIs', [name] or [name]. All information received on the participant will be stored on a UAB Department of Orthodontics owned encrypted computer locked in the PI's office. At the end of the study, the data will be stored on the UAB School of

Dentistry's server. All participants will be notified if any data is lost or stolen or any risks develop after they have consented to participate in the study.

- c. If hazards occur that might make the risks of participation outweigh the benefits for all participants, describe (i) the criteria that will be used to stop or end the entire study and (ii) any special procedures, precautions, or follow-up that will be used to ensure the safety of currently enrolled participants.  
If the foreseeable hazards to the participants outweigh the benefits of continuing the study, the study will be stopped. All participants will be notified if any risks develop after the have consented to participate in the study. All currently enrolled participants will be able to discontinue participation at any time without penalty.

## 20. Informed Consent

- a. Do you plan to obtain informed consent for this protocol? Yes No  
**If Yes**, complete the items below.  
**If No**, complete and include the [Waiver of Informed Consent](#) or [Waiver of Authorization and Informed Consent](#), as applicable.
- b. Do you plan to document informed consent for this protocol? Yes No  
**If Yes**, complete the items below.  
**If No**, complete the items below **and** include the [Waiver of Informed Consent Documentation](#).
- c. How will consent be obtained? The informed consent documents will clearly state the purpose of the study, description of the procedure, associated risks, benefits, and alternatives, the ability to refuse to participate in the study or discontinue participation at any time without penalty. Each participant will be given time to read the informed consent and ask questions if necessary.
- d. Who will conduct the consent interview? PI, Co-PI, or Research Coordinator
- e. Who are the persons who will provide consent or permission? Patients and parents of minor participants.
- f. What steps will be taken to minimize the possibility of coercion or undue influence? During the consent process, participants will neither be encouraged nor discouraged to be involved with the trial. Participants will be fully informed of the risks, benefits, and alternatives to participating in the trial. Also, they will be allowed to withdraw from the trial at any time.
- g. What language will the prospective participant or the legally authorized representative understand? English
- h. What language will be used to obtain consent? English
- i. If any potential participants will be, or will have been, in a stressful, painful, or drugged condition before or during the consent process, describe the precautions proposed to overcome the effect of the condition on the consent process. If not, enter "no such effect."  
No such effect.
- j. If any project-specific instruments will be used in the consenting process, such as flip charts or videos, describe the instrument(s) here, and provide a copy of each. If not, enter "not used."  
Not used

- k. How long will participants have between the time they are told about the study and the time they must decide whether to enroll? If not 24 hours or more, describe the proposed time interval and why the 24-hour minimum is neither feasible nor practical. 24 hour

## 21. Procedures to Protect Privacy

Describe the provisions included in the research to protect the privacy interests of participants (e.g., others will not overhear your conversation with potential participants, individuals will not be publicly identified or embarrassed).

Participants will be taken to a private area in UAB's orthodontic clinic and will be fully informed about the risks, benefits, and alternatives of participating in the clinical trial. The participants will be allowed to ask questions prior to signing the consent form.

## 22. Procedures to Maintain Confidentiality

- a. Describe the manner and method for storing research data and maintaining confidentiality. If data will be stored electronically anywhere other than a server maintained centrally by UAB, identify the departmental and all computer systems used to store protocol-related data, and describe how access to that data will be limited to those with a need to know.

Participants will be given a unique code that is linked to the name. The code will be assigned at the time the consent form is signed and only known by the listed staff involved in research. Images, intraoral photographs, codes, and names will be stored on a UAB Orthodontic Department owned encrypted computer. This computer will be locked in the PI's office and will only be accessible to those directly involved in the study. At the end of the study, all data will be stored on the UAB School of Dentistry's server.

- b. Will any information derived from this study be given to any person, including the subject, or any group, including coordinating centers and sponsors?  Yes  No  
If Yes, complete i-iii.

- i. To whom will the information be given? [name], CEO of Aerodentis  
ii. What is the nature of the information? Intraoral and extraoral photos, tooth movement measurements, compliance data, quality of life questionnaire.  
iii. How will the information be identified, coded, etc.? Each patient will be assigned a unique patient ID, solely for research purposes.

## 23. Additional Information

In the space below, provide any additional information that you believe may help the IRB review the proposed research, or enter "None."

Attached forms:

-Protocol oversight Review Form

-Informed consent

-Appendix A, picture of Aerodentis console

- Compliance questionnaire

- Quality of life questionnaire

- Device review sheet

- Aerodentis user guide

- Aerodentis system risk analysis

- Aerodentis Proposal

Statistical Analysis Plan

Title of Research: Aerodentis Clinical Trial: Assessment of the Efficacy of

Orthodontic Tooth Movement Using the Aerodentis System

UAB IRB Protocol #: F160418007

Principal Investigator: [name] [name], BDS, MScD, PhD.

Co-investigators: [name], DMD, PhD

[name], DDS

Sponsor: Dror Orthodesign Ltd.

[name]

[name]

[name]

Statistical Considerations

Overview and Rationale for Primary Parameter

The aims of this trial are to assess the safety and efficacy of the Aerodentis system in producing tooth movement. Safety is measured by absence of root resorption while efficacy is typically measured by various parameters relating to tooth movement. Because tooth movement is highly variable between individuals, treatment success is not usually contingent on a specific amount of movement over time. To this end we specify the primary endpoint, achieving score <1mm in Little's index

Design

Historical controls will be utilized as a comparator group. This historical data will be generated using the same inclusion/exclusion criteria as the proposed prospective single arm study. The historical patient population will be derived from the study sites participating in this prospective study. The study inclusion/exclusion criteria will be applied to consecutive patients treated with clear correctors that have the potential for complete datasets (as defined by the study protocol).

The use of single arm, open label trial with historical controls is supported when a device technology is well developed and the subject of interest is well understood^[1]. Orthodontic treatment of this patient population (i.e., use of mechanical force) is well developed and understood. In addition, the primary

Page 1 of 3

Version Date: 9/27/2016

^[1] Draft Guidance for Industry, Clinical Investigators, and Food and Drug Administration Staff Design Considerations for Pivotal Clinical Investigations for Medical Devices, published August 15, 2011.

endpoints of success are Objective Performance Criteria (OPC) (use of impressions to objectively measure tooth movement and Little's index scoring and independent radiographic evaluation of tooth resorption). The effectiveness OPC in the treatment of this patient population is a summative Little's index score of <1.5mm. The safety OPC is to allow for no tooth root resorption. The use of this study design is supported both by proposed FDA Gudiance⁵ and recent FDA approvals of devices with a high risk profile^[2]

Safety Analysis Set

The safety analysis set will consist of all patients from whom dental plaster impressions were taken for the purpose of treatment with Aerodentis.

Full Analysis Set

Primary efficacy analysis will be assessed using the Full Analysis Set (FAS). The FAS will consist of patients from the intent to treat (ITT) cohort who started treatment and have at least one post-baseline assessment, and have no major protocol violation as determined by blind review.

Missing Data:

Missing data will be handled for imputation the primary endpoint data for FAS subjects. Subjects with no post-baseline assessment will be imputed as failures and will not be included in the FAS population. The MMRM model (Mixed-effect Model for Repeated Measures), which is based on MAR (missing at random) assumption will be applied to all the subjects of the FAS population. Sensitivity analyses will be applied for testing the effect of the imputation on the treatment effect. This will show the influence of the imputation on the study results.

Per Protocol Analysis Set

Efficacy analyses will also be done on the Per Protocol subset. Per Protocol subset include all FAS subjects who completed the study according to the protocol with no protocol deviations.

Missing Values: Only observed data will be used in the Per Protocol Analysis Set; i.e. missing data will not be imputed.

Endpoints

Safety

The safety endpoints are adverse events, whether or not treatment related. Included will be amount of root repsorption, measured by comparing x-rays before, mid-point and after treatment

Primary Efficacy

The primary endpoint will be to evaluate the degree of tooth movement. Treatment success will be defined using the Little's Index and when a score does not summative exceed 1.5mm (<1.5mm)

YGgDw&usg=AFQjCNGQWAFNwDj6XKq5ZVay8hssRm9lzA&bvm=bv.51156542,d.cWc

Page 2 of 3

Version Date: 9/27/2016

^[2] Campbell, Greg Some Considerations for Medical Devices: Historical Controls and Performance Goals, FDA-NIH Science of Small Clinical Trials Course. November 27-28, 2012

https://www.google.com/url?sa=t&rct=j&g=&esrc=s&source=web&cd=15&cad=rja&ved=0CEIQFjAEOAo&url=https%3A%2F%2 Fevents-support.com%2FDocuments%2FCampbell.pdf&ei=OL4dUvnoLMK9sAT7-

This is a reasonable endpoint as the results are comparable to other successful aligner studies. In addition, studies to long term stability have used 2mm or less as an acceptable outcome of success post orthodontic treatment.

Invisalign® treatment in the anterior region: were the predicted tooth movements achieved? Krieger E¹, Seiferth J, Marinello I, Jung BA, Wriedt S, Jacobs C, Wehrbein H. http://www.ncbi.nlm.nih.gov/pubmed/22890691

How well does Invisalign work? A prospective clinical study evaluating the efficacy of tooth movement with Invisalign. **Kravitz** 2009

http://www.ncbi.nlm.nih.gov/pubmed/19121497

Semin Orthod. 1999 Sep;5(3):191-204.

Stability and relapse of mandibular anterior alignment: University of Washington studies. Little RM.

Br J Orthod. 1990 Aug;17(3):235-41.

Stability and relapse of dental arch alignment.

Little RM1.

Sample Size Considerations

The planned sample size is 40 subjects. The tested group will include 40 subjects.

Study Hypotheses

We will have demonstrated success if the summative Little's index score will achieve score <1.5mm.

Statistical Analysis

All measured variables and derived parameters will be tabulated by descriptive statistics.

For categorical variables summary tables will be provided giving sample size, absolute and relative frequency and 95% CI (Confidence Interval) for proportions.

For continuous variables summary tables will be provided giving sample size, arithmetic mean, standard deviation, median, minimum and maximum and 95% CI (Confidence Interval) for means of variables.

Complete individual listings of all data represented in the CRF will be provided as an appendix. All calculated and derived variables will be listed as well.

All tests will be two-tailed, and a p value of 5% or less will be considered statistically significant. All statistical analyses will be performed and data appendices will be created using the SAS® system Version 9.1.3 or higher.

The effects of noncompliance, dropouts, and covariates on treatment will be assessed to determine the impact on the general applicability of results from this study.

Page 3 of 3

Version Date: 9/27/2016

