#### **15. Participants (Screening and Selection)**

a. How many participants are to be enrolled at UAB? 45, 30 active and 15 control

If multi-center study, total number at all centers: \_\_\_\_\_

b. Describe the characteristics of anticipated or planned participants.

Sex: male and female

Race/Ethnicity: all races

Age: 12-60 with adult dentition (permanent teeth)

Health status: medically fit and well

*Note. If data from prior studies indicate differences between the genders or among racial/ethnic groups in the proposed research or if there are no data to support or to negate such differences, Phase 3 clinical trials will be required to include sufficient and appropriate entry of gender and racial/ethnic subgroups so that trends detected in the affected subgroups can be analyzed. If ethnic, racial, and gender estimates are not included in the protocol, a clear rationale must be provided for exclusion of this information. If prior evidence indicates that the results will not show gender or racial differences, researchers are not required to use gender or race/ethnicity as selection criteria for study participants. They are, however, encouraged to include these groups. See Section II. Policy of the NIH POLICY AND GUIDELINES ON THE INCLUSION OF WOMEN AND MINORITIES AS SUBJECTS IN CLINICAL RESEARCH – Amended, October, 2001) for further details.*

c. From what population(s) will the participants be derived?

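### The SAP sets the primary success cut-off at <1 mm in one place and <1.5 mm in three others, so patients scoring between the two are failures or successes depending on which sentence is used.

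*SAP*

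**What the plan says.** The SAP (version date 9/27/2016) states the success criterion four times.

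- Overview and Rationale for Primary Parameter: "To this end we specify the primary endpoint, achieving score <1mm in Little's index".
- Design, on the objective performance criterion (OPC): "The effectiveness OPC in the treatment of this patient population is a summative Little's index score of <1.5mm".
- Endpoints, Primary Efficacy: "Treatment success will be defined using the Little's Index and when a score does not summative exceed 1.5mm (<1.5mm", where the bracket closes after the figure.
- Study Hypotheses: "We will have demonstrated success if the summative Little's index score will achieve score <1.5mm".

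After the Primary Efficacy definition the SAP adds, as support from the literature, that "studies to long term stability have used 2mm or less as an acceptable outcome of success post orthodontic treatment". That is background and not a fifth cut-off for this trial. The protocol describes assessments of tooth movement (sections 13 and 16) but names neither Little's index nor a success threshold.

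**The concern.** The cut-off is the trial's decision rule. The Study Hypotheses section consists only of reaching the score, and the SAP states no performance goal, margin or power beside it. If the cut-off has two values, the primary result has two values.

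The setting makes this more serious. The study is open label (protocol section 13) and funded by the device company (protocol section 4), and outcomes are assessed every 4 weeks. Scores therefore accumulate in view of the people running the trial. With both figures on paper, either could be cited in good faith once the data are known, and a reader could not tell whether the reported success rate was the one planned.

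There is also a smaller conflict inside the Primary Efficacy sentence. Its words count exactly 1.5 mm as a success, while its bracketed sign counts it as a failure.

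**Working it through.** **Step 1: set the statements side by side.**

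| SAP section | Cut-off | Summative score named? | Exactly 1.5 mm |
|---|---|---|---|
| Overview and Rationale | <1 mm | no | failure |
| Design (OPC) | <1.5 mm | yes | failure |
| Primary Efficacy | 1.5 mm | yes | success by the words, failure by the bracket |
| Study Hypotheses | <1.5 mm | yes | failure |

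The count is one statement at 1 mm and three at 1.5 mm. All are current text on pages with the same version date, and none comes from a change log. No rule of precedence is given, and no second, stricter endpoint is described that would explain the 1 mm figure.

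**Step 2: find who is affected.** Below 1.0 mm, all four statements give success. Above 1.5 mm, all four give failure. From 1.0 mm to just under 1.5 mm, the overview gives failure and the other three give success. Exactly 1.5 mm depends on the boundary reading.

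**Step 3: look for a figure to reproduce.** The only design figure is the sample size, "The planned sample size is 40 subjects. The tested group will include 40 subjects". No assumed success rate comes with it, so it cannot be traced to either cut-off. The protocol gives a different number (section 15a): "45, 30 active and 15 control". That discrepancy is a separate matter, so both denominators are used below.

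**Step 4: illustrate the size.** Let F be the distribution function of the final score. The gap in success rate is F(1.5) − F(1.0). Assumed, not from the documents: a gamma distribution with shape (mean/SD)² and scale SD²/mean, means 0.6, 0.8, 1.0, 1.2 and 1.5 mm, and SDs 0.4, 0.6 and 0.8 mm.

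| Mean, SD (mm) | Rate at <1 mm | Rate at <1.5 mm | Gap (points) | Of 30 | Of 40 |
|---|---|---|---|---|---|
| 0.6, 0.8 (smallest gap) | 80.3% | 89.0% | 8.7 | 2.6 | 3.5 |
| 1.2, 0.6 | 42.7% | 73.5% | 30.8 | 9.2 | 12.3 |
| 1.2, 0.4 (largest gap) | 33.8% | 78.9% | 45.1 | 13.5 | 18 |

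**Step 5: vary the assumption.** Gamma and lognormal distributions with means 0.75 to 1.5 mm and SDs of 0.5 or 0.75 mm put 12% to 43% of patients in the band. That is about 3.5 to 13 of 30, or 5 to 17 of 40. If scores sit far below both cut-offs the gap shrinks: a gamma with mean and SD both 0.3 mm gives 96.4% against 99.3%, about 3 points.

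**Step 6: compare with sampling error.** The 95% CI half-width for a proportion is 1.96 × √(p(1−p)/n). At n = 40 it is 1.96 × √(0.9 × 0.1/40) = 9.3 points for p = 0.9, and 1.96 × √(0.5 × 0.5/40) = 15.5 points for p = 0.5. Over much of the assumed range, the choice of cut-off moves the result by more than chance would.

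**The case against.** The best reply is that the two figures do not carry equal weight. The three sections that define the analysis all use 1.5 mm, and the 1 mm figure appears once, in an introductory rationale, so it may be a leftover. That is a plausible reading and it supports aligning to 1.5 mm. It does not remove the conflict, because the 1 mm sentence is the one that expressly specifies the primary endpoint. Counting sections is a reader's inference, not pre-specification.

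Other points stand in part:

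- **Scale.** The overview does not say that the score is summative, so its 1 mm might be meant on another scale. The SAP does not say so, and the endpoint would then still be defined in two ways.
- **Boundary.** An at-most sign could have lost its bar when the PDF was read. This is possible but not shown. The boundary point is minor, and the continuous model above gives it no weight.
- **Size.** Every distribution used is assumed, and the true gap could lie outside the range shown.
- **Protocol.** The form is written in lay language and lists a proposal among its attachments (section 23) that is not in the text reviewed. A cut-off may be stated there.
- **Sufficiency.** The Study Hypotheses section does not say whether the score applies to each patient or to a group mean, nor what success proportion is required. A single cut-off is necessary, but it does not by itself complete the decision rule.

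**Conclusion.** The concern holds and must be fixed. The SAP gives two values for the primary success cut-off, and nothing in the documents reviewed settles which applies. This conclusion rests on the text alone and needs no distributional assumption.

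The size is illustrative: 9 to 45 percentage points on the assumed gamma grid. Only patients from 1.0 to just under 1.5 mm change status, apart from any at exactly 1.5 mm. Choosing a cut-off after seeing the data is a risk that the wording leaves open. The documents do not show that it has happened or is intended.

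**What to change.** State one cut-off, one scale and one boundary rule in all four places.

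1. In the overview, replace the 1 mm figure with a summative Little's index score <1.5 mm, matching the OPC and hypothesis sections.
2. Rewrite the Primary Efficacy sentence so that success is a summative score <1.5 mm and exactly 1.5 mm is a failure. Removing words from the present sentence would not leave a readable definition.
3. Have the sponsor confirm that 1.5 mm with a strict boundary is what was intended. Three sections point that way but do not prove it. If another value was meant, carry that one through instead.
4. Report the success rate at <1 mm as a named secondary or sensitivity result. This is useful for transparency but is not needed to remove the contradiction.
5. Put the same definition in protocol section 16.
6. Date the change before any post-baseline score is read. If scores have already been read, say so and report both rates.

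The cost is a few words in the SAP and one line in the protocol. No change to data collection is needed.

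### Zero cases of root resorption in 30 or 40 patients would not show its absence, and the SAP does not tie this safety criterion to a confidence limit

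*SAP*

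**What the plan says.** The SAP's overview of the primary parameter states: "Safety is measured by absence of root resorption". Its Design section says that the primary "endpoints of success are Objective Performance Criteria (OPC"), names independent radiographic evaluation of resorption as one of them, and adds: "The safety OPC is to allow for no tooth root resorption". Under Endpoints, Safety, it also plans a graded measurement: "Included will be amount of root repsorption, measured by comparing x-rays before, mid-point and after treatment".

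For this criterion the SAP gives no unit of count (patient, tooth or root), no threshold for calling resorption present, no acceptable rate and no confidence limit. Its Statistical Analysis section does plan 95% confidence intervals for proportions and for means across all measured variables. Its Study Hypotheses section names only Little's index as the condition for success.

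The two documents give different sizes for the device group. The SAP states: "The planned sample size is 40 subjects. The tested group will include 40 subjects". Protocol section 15.a states: "45, 30 active and 15 control". The safety denominator is defined by impressions, not by x-rays: "The safety analysis set will consist of all patients from whom dental plaster impressions were taken for the purpose of treatment with Aerodentis".

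**The concern.** A criterion worded as absence invites a conclusion of absence. With 30 or 40 patients, a clean set of x-rays is compatible with a rate that a reader might not regard as negligible. If the trial reports that the safety criterion was met and goes no further, it claims a property that the data cannot show.

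A zero-event criterion has a second weakness if it is applied to the study as a whole: the chance of meeting it falls as more patients are enrolled. The same device would then be more likely to meet the criterion under the protocol's number than under the SAP's, for reasons unrelated to the device.

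At stake is what may be concluded on one of the SAP's two success criteria. The graded x-ray data that could support a better statement are already to be collected in the device group.

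**Working it through.** **Inputs.** The device group is n = 30 (protocol section 15.a) or n = 40 (SAP, Sample Size Considerations). The criterion is zero cases (SAP, Design). The confidence level is 95%, two-sided (SAP, Statistical Analysis). The documents give no expected or acceptable resorption rate, so the true rates below are assumptions shown as a range. They assume one count per patient, because the SAP names no unit.

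**The plan's own figure.** The SAP's 40 comes with no rate, power, margin or dropout. It can be neither reproduced nor refuted, and nothing here says that 40 is wrong.

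**Step 1: what zero cases exclude.** The exact (Clopper-Pearson) two-sided 95% upper limit after 0/n is 1 − 0.025^(1/n).
- n = 30: 1 − 0.025^(1/30) = 0.116, or 11.6%.
- n = 40: 1 − 0.025^(1/40) = 0.088, or 8.8%.

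The one-sided 95% limits, 1 − 0.05^(1/n), are 9.5% and 7.2%.

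**Step 2: fewer evaluable patients.** The safety set includes anyone who had impressions taken, including patients who may never have a follow-up x-ray. If, as an illustration, only 25 patients had follow-up films, the two-sided limit after zero cases would be 1 − 0.025^(1/25) = 0.137, or 13.7%.

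**Step 3: dependence on n, if the criterion is a study-level count rule.** The chance of zero cases is (1 − p)^n.

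| Assumed true patient-level rate p | n = 30 | n = 40 |
|---|---|---|
| 1% | 0.99^30 = 74% | 0.99^40 = 67% |
| 2% | 0.98^30 = 55% | 0.98^40 = 45% |
| 5% | 0.95^30 = 21% | 0.95^40 = 13% |

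At each rate the larger group is less likely to show zero cases. Counting by tooth would lower these chances further if the per-tooth rate were the same as p, because each patient contributes several teeth.

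**Step 4: scale.** The number of evaluable patients, all without a case, that brings the two-sided upper limit to u or below is ln(0.025)/ln(1 − u), rounded up. For u = 10% it is 36 and for u = 5% it is 72. These are given for scale only. Neither is proposed as a target.

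**The case against.** **No written rule fails the device on one case.** A reader might infer that a single case ends in failure. The SAP does not say so. The companion effectiveness criterion is a score that an individual patient attains, so the safety criterion may likewise be an individual one, and the only stated success hypothesis concerns Little's index. This objection stands. The count rule is the plain reading of a criterion that allows none, but it remains a reading, and Step 3 is conditional on it. On the other reading, a primary criterion has no study-level threshold, which also needs to be clarified. Steps 1 and 2 hold either way.

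**No wrongful failure is shown.** One might say that the rule wrongly fails a device with a 1% or 2% rate. That presupposes such a rate is acceptable, and the documents give no acceptable rate. Taken literally, a device with any true resorption does not meet a criterion of none. The table therefore shows only how the outcome varies with the rate and with n.

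**Intervals are already planned.** This is correct. The SAP's general intervals would cover both the proportion with resorption and its amount, so it would be wrong to say that the uncertainty goes unreported. What is missing is a link between those intervals and the safety criterion, and a stated exact method.

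**Reading error.** The SAP plans independent radiographic evaluation, and the documents give no error rate, so a claim that misreadings would decide the result has no support. Independent reading does not, however, supply the missing threshold for calling resorption present.

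**Comparison with controls.** A reader might think that the difference from clear aligners can be reported at once. The documents do not secure the data. The safety set is limited to Aerodentis patients, the procedure table in protocol section 16.e lists no x-rays for either group, and the SAP's controls are historical, with no text securing their mid-point films.

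**Conclusion.** The concern holds in a limited form. The SAP states a primary safety criterion as absence, and zero cases in the planned group would not show absence: rates up to 11.6% (0/30) or 8.8% (0/40) would remain within the exact two-sided 95% interval, and higher rates if fewer patients are evaluable. This rests on a patient-level count, on independent patients, and on every patient in the stated number having follow-up x-rays.

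The dependence on enrolment applies only if the criterion is a study-level count rule, and its size rests on assumed rates. The documents do not support going further and saying that an acceptable device would be failed, that the sample size is wrong, or that the investigators will report zero cases as proof of absence. The change is worth making because it alters what the trial can conclude and takes little effort.

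**What to change.** In the SAP:

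1. Define the unit of count and the threshold for calling resorption present on x-ray. State whether the criterion applies to each patient or to the study as a whole.
2. Base the safety conclusion on the proportion of patients with resorption among Aerodentis patients with follow-up x-rays, with an exact (Clopper-Pearson) 95% confidence interval, and on the amount of resorption with its 95% interval.
3. State that zero cases will be reported with the upper limit for the actual evaluable number, and not as absence of resorption.
4. Report the comparator proportion and the between-group difference only where comparable control x-rays exist.
5. Reconcile the 30 in the protocol with the 40 in the SAP before any limit is quoted.

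If an acceptable rate is wanted, the sponsor and investigator must set and justify it. None is proposed here.

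The cost is SAP wording and one table from x-rays that the SAP already plans in the device group. Item 4 adds work only if usable control films are found. The downside is a less clear-cut pass/fail safety statement.
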